5B.1. Project Life Force Clinical Intervention:

is a manualized, weekly 90-minute group treatment lasting 3 months coinciding with the time frame for enhanced monitoring of Veterans identified as “high-risk”. Session content is described in **Table 1**. The use of DBT skills⁹ in PLF differs from other DBT interventions in that it focuses primarily

on emotion regulation (ER), distress tolerance and interpersonal effectiveness *in the specific context of implementing a safety plan*. Mindfulness is not covered. PLF is augmented with additional skill modules on strengthening friendships and education pertaining to suicide risk, suicide means restriction and suicide prevention mobile Apps.

This is an open-group format, with new members joining throughout the 12-week cycle to allow immediate access to the skills and accommodate the need for expeditious safety planning for higher risk Veterans. While traditional DBT skills groups enter patients at designated points (e.g. the beginning of new skills modules), there is a growing evidence base of the effectiveness of DBT skills groups offered in more flexible frameworks, including drop-in formats¹⁵. Our open-group framework facilitates ease of entry. Since the program runs continuously, Veterans who join after session #1, can pick up any missed material in the next cycle. This project will randomize subjects over a one-year time frame to 12 weeks of either TAU or PLF. The study will include 4 cycles of the PLF intervention. See **Appendix 2** for PLF handouts and more detail on individual session lesson plans. PLF session format will be modeled after DBT skills groups and include: 1) brief check in and any follow up pertaining to use of the safety plan, 2) homework review, 3) teaching of new material and skill, 4) in-class practice of the skill, and 5) assignment of homework/ outside practice/development of safety plan.

5B.2. Finalize PLF manual: With input and feedback from co-investigators Drs. [name] (SSP original developer), [name] (clinical trial development, family interventions), [name] (DBT, psychotherapy engagement), [name] (health services, implementation) and [name] (PCC Director), the PI will finalize the PLF manual and associated handouts. We will also create a tool for assessing fidelity to PLF (see **5C.3.1**).

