5C.3. Experimental Condition- PLF. The pilot will use the PLF intervention finalized during Phase 1a of the proposed project. PLF is a 90-minute, 12 sessions, held weekly run by two clinicians using the final version manual and handouts from Phase 1a (see research plan, **5B.1**, and **appendix 2** for current version) with the stated purpose of developing, refining and implementing the SSP. The treatment is adjunctive and SSPs developed in the PLF Intervention will be shared with the Veteran's treatment team for feedback/approval. Veterans randomized to PLF will continue with their psychiatrist, case manager and services by the suicide prevention coordinator as indicated.

5C.3.1. PLF Training and Fidelity. Our research team (Drs. [name], [name], [name]) has experience developing psychosocial interventions and establishing their fidelity. Similar to our DBT RCT for suicidal Veterans (see **preliminary work**, section 4.2), PFL training will include weekly supervision with therapists and videotaping and review of sessions for fidelity using an objective scale. This adherence scale will be finalized with assistance by [name] during phase 1a of the project, and include ratings along a 5 point Likert scale (0- unacceptable, 5- excellent) assessing core features of the framework, content and principles of the treatment for each session along with competence variables including ability to manage the group, build rapport, manage crises. For the PLF RCT (phase 2), ratings will be performed by an independent rater on randomly selected group sessions. Overall ratings require an average score of 4 or above for adequate adherence to the intervention.

5C.4 Comparison Condition- TAU. The comparison condition, treatment as usual (TAU) will consist of the standard treatment delivered to suicidal Veterans in the VA including visits with the outpatient psychiatrist and case manager, with content of sessions and treatment appointment intervals determined by the subject's treatment team and suicide prevention coordinator's suggestions.

5C.5. Randomization Procedure. After the baseline assessment, participants will be informed of their assigned condition. Subjects will be assigned to study group using a blocked randomization plan with blocks of random sizes. Block sizes will be of either 2, or 4. The blocking will aid in keeping investigators blinded to study group assignment. A total of 20 Veterans are randomized to each group.

5C.6. Participant Assessment.

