5D.4. Quantitative Analytic Strategy: Efficacy. We will first explore if any demographic features (e.g. gender, chart diagnosis) influence number of sessions attended and will include these demographic variables as covariates in our analyses where appropriate. The primary endpoint is self-reported suicidal ideation and secondary endpoints include self-reported measures of depression, hopelessness, reasons for living, and a treatment utilization measure of number of outpatient mental health visits attended. All of these metrics, except for treatment utilization, are continuous scales that will be measured at baseline and again at months 1, 3, and 6. For these outcomes, linear mixed models for longitudinal data²⁸ will be used for analysis. In these models, the fixed effects will be time, treatment group, and the interaction between time and treatment. The random effects will be the subjects. The interaction term in each model will test whether the trend in response over time differs between the treatment groups. The last secondary outcome, number of outpatient mental health visits attended, measures counts. A Poisson regression model will be fit to these data using Generalized Estimating Equations (GEE)²⁸ and the model will allow for testing whether the rate of outpatient visits for mental health differs between the two treatments. All statistical tests will be two-tailed with an alpha =.05.

For the Exploratory Aim, an Analysis of Covariance model with an interaction term will be used. In this model the outcome variable will be the CRIS-CAT score, the binary treatment variable will be whether the subject received PLF or TAU, the covariate will be the BSI, and the interaction will be that between the treatment variable and the Beck scale covariate. If there is no interaction, then the focus will be on the treatment effect. In this situation the regression lines relating CRIS-CAT to BSI will be parallel, and the treatment effect will measure the distance between the parallel lines providing a measure of the improvement in community integration over the entire range of the BSI in subjects receiving PLF compared to patients receiving TAU. On the other hand, if there is a significant interaction, this will correspond to a situation of intersecting regression lines for the two treatment groups. In such a circumstance, the improved community integration of one treatment group will be limited to a sub-range of the Beck scale.

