5D.5. Power and Sample Size Justification.

Although this is a pilot study with the purpose of investigating feasibility and collecting preliminary data to aid in planning a larger study, power calculations were carried out for the proposed sample size of 40 enrollees. With 20 subjects randomized to each of the two treatment groups, there will be 80% power to detect an effect size of 0.91. We recognize that this effect size is probably larger than the true effect size for these treatments, but one of the outcomes of this pilot trial will be the data allowing us to improve the required sample size estimates for a future study.

Figure 2--Study Time Line

6) Time Line. (See Figure 2)

RCT Recruitment is ongoing and Veterans can enter at any point during the RCT. During this time frame, we expect to recruit 4-5 Veterans/month from both inpatient and outpatient services.

activity	Month 1-6		Month 7-12		Month 13-18		Month 19-24	
Hire/train staff								
Finalize Manual & Obtain IRB approval								
Conduct RCT								
Conduct follow-ups								
Data analysis/papers

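### With subject as the only named random effect, the time-by-treatment test can be anti-conservative if correlation decays or individual slopes vary; 5D.4 should state the time coding and a fuller within-subject covariance

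*Combined protocol and SAP*

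**What the plan says.** Section 5D.4 of the combined protocol and SAP gives the model for all outcomes measured on continuous scales: "the fixed effects will be time, treatment group, and the interaction between time and treatment", followed by "The random effects will be the subjects". The interaction is the test of efficacy, described as a difference between arms in trend over time. Visits are at baseline and months 1, 3 and 6. On the test level: "All statistical tests will be two-tailed with an alpha =.05".

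Section 5D names no random slope, residual covariance structure, robust standard error, or term for therapy group, cycle or clinician. It does not say whether time is linear or categorical. Section 5D.2 handles missing visits by direct likelihood within the same model.

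On delivery, section 5C.3 says "PLF is a 90-minute, 12 sessions, held weekly run by two clinicians" and section 5B.1 says "This is an open-group format, with new members joining throughout the 12-week cycle", with four cycles over the study. TAU (section 5C.4) is care from the Veteran's own treatment team, with no study group.

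**The concern.** A subject random intercept on its own makes scores one month apart exactly as correlated as scores six months apart, and lets individuals in an arm differ in level but not in underlying slope. The plan gives reason to doubt both. Section 5C.6.3 treats the first four weeks as the period of highest risk and month 3 as the time after acute symptoms have settled, so Veterans are likely to change at different rates.

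When correlation falls with time or slopes vary, the pooled residual understates the variance of a slope difference. Two uses of the trial would suffer: the preliminary efficacy statement, which rests on a two-sided 5% test, and the planning of the next study, which would inherit intervals that are too narrow. Direct likelihood also leans on the covariance when visits are missed. The team's earlier trial (section 4.2) had 59% completing its 6-month treatment.

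Separately, PLF Veterans share a group and clinicians and TAU Veterans do not, so PLF outcomes may be correlated with one another.

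**Working it through.** **1. The plan's own figure.** Section 5D.5 states "With 20 subjects randomized to each of the two treatment groups", "there will be 80% power to detect an effect size of 0.91". A two-sided two-sample t-test has 38 df and noncentrality 0.91 x sqrt(20/2) = 2.878. Power is 80.1% and the minimum detectable effect is 0.909, so the figure reproduces. It describes one comparison of independent means. Repeated visits and clustering do not enter it.

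**2. Inputs.** From the documents: 20 per arm; visits at 0, 1, 3, 6 months; BSI test-retest correlation 0.54 (5C.6.3a, interval not given). Assumed: decay rates, slope SDs, ICCs, unit variance, complete data.

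**3. Linear time, random intercept.** The mean visit time is 2.5, the deviations c are -2.5, -1.5, 0.5, 3.5, and S = 6.25 + 2.25 + 0.25 + 12.25 = 21. For within-subject covariance V:

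- q = c'Vc, and the true variance of one subject's slope is q/S^2
- w = trace(V) - (sum of all entries of V)/4
- residual df = 160 - 40 - 2 = 118, and expected residual mean square MS = (40w - 2q/S)/118
- ratio of model SE to true SE = sqrt(MS x S/q)
- type I error is approximately 2[1 - Phi(1.980 x ratio)]

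Worked row, correlation 0.54 per month. The off-diagonal entries at gaps of 1, 2, 3, 3, 5 and 6 months are 0.540, 0.292, 0.157, 0.157, 0.046 and 0.025, which sum to 1.217. Then w = 4 - (4 + 2 x 1.217)/4 = 2.391; q = 21 + 2 x 1.427 = 23.85; MS = (95.66 - 2.27)/118 = 0.791; ratio = sqrt(0.791 x 21/23.85) = 0.83; type I error about 9.8%. Simulation under the null (20,000 trials) gives 10.2%.

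| Assumed truth | w | q | MS | SE ratio | Type I, formula | Type I, simulated |
|---|---|---|---|---|---|---|
| Constant 0.54 | 1.380 | 9.66 | 0.460 | 1.00 | 4.8% | 5.1% |
| Decay 0.54 | 2.391 | 23.85 | 0.791 | 0.83 | 9.8% | 10.2% |
| Decay 0.8 | 1.473 | 18.52 | 0.484 | 0.74 | 14.2% | 14.6% |
| Decay 0.9 | 0.855 | 11.76 | 0.280 | 0.71 | 16.1% | 16.6% |
| 0.4 constant + 0.4 decaying at 0.7 + 0.2 noise | 1.368 | 13.01 | 0.453 | 0.86 | 9.0% | 9.3% |
| Slope SD 0.05 | 1.433 | 10.76 | 0.477 | 0.96 | 5.6% | about 6% |
| Slope SD 0.10 | 1.590 | 14.07 | 0.528 | 0.89 | 7.9% | 8.1% |
| Slope SD 0.15 | 1.853 | 19.58 | 0.612 | 0.81 | 10.9% | 10.8% |

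Slope SDs are in outcome SDs per month. The formula columns in those rows take residual variance 0.46 (1 - 0.54), so that w = 3 x 0.46 + 21s^2 and q = 21 x 0.46 + 441s^2. Across decay rates from 0.50 to 0.95 the simulated range is 9.4% to 17.6%. A t-test on each subject's own fitted slope stays at 4.8-5.3% under constant or decaying correlation, so the inflation comes from the covariance assumption and can be avoided.

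**4. Categorical time, same decay.** The residual mean square is now w/3. At 0.54 per month it is 2.391/3 = 0.797. For the month-6 contrast with baseline the SE ratio is sqrt(0.797/(1 - 0.025)) = 0.90; for month 1 it is sqrt(0.797/(1 - 0.54)) = 1.32. Simulated results for decay 0.50 to 0.95:

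| Test | SE ratio | Type I |
|---|---|---|
| Overall 3-df interaction | - | 5.3% to 7.2% |
| Month 6 | 0.92 to 0.76 | 7.2% to 13.9% |
| Month 3 | 0.97 to 1.04 | 5.8% to 4.3% |
| Month 1 | 1.29 to 1.75 | 1.2% to 0.1% |

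**5. Shared PLF group.** Four cycles and 20 PLF Veterans give about m = 20/4 = 5 entrants per cycle. With a cycle effect on post-baseline scores and constant within-subject correlation, the simulated linear-time interaction has type I error 6.1% at ICC 0.05 and 6.5% at ICC 0.10; the 3-df test gives 6.6% and 7.0%. A second run gave 5.6-6.8% for the same settings. A cycle effect equal at every visit, baseline included, cancels (5.0%). For the t-test behind the stated power, the PLF-arm design effect is 1 + 4 x 0.05 = 1.2 or 1 + 4 x 0.10 = 1.4, and power at 0.91 becomes 76.2% or 72.6%.

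**The case against.** A reader might infer that the standard errors simply are too small and that the planned 5% test is not one. The documents do not support this. They give no decay rate, slope SD or ICC; with constant correlation and no clustering the test is sound; and 5D.4 neither fixes time as linear nor expressly excludes a random slope or structured residuals. The word trend points to linear time but does not settle it. If time is categorical, the overall test is nearly nominal and the month-1 comparison errs the other way, so not every error favours PLF. The higher figures also need strong pure decay. All of this stands, and it is why the size is given as a range that includes the harmless case.

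A reader might also treat all 20 PLF Veterans as one cluster and report a large inflation. An effect common to the whole PLF arm is confounded with PLF, and no random effect could remove it, so it is not a fault of this model. Nor does entry cycle form a clean cluster, because membership overlaps.

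Finally, this is a 40-person pilot, and section 5D.5 concedes that the detectable effect is probably larger than the true one. That lowers the stakes. It does not remove the point: a two-sided 5% test is still planned, and the data are meant to inform the next sample size. If a fuller covariance was intended, it still has to be written down.

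**Conclusion.** The point holds in conditional form, and the change should be made. Under the ordinary reading of 5D.4, the interaction test is exposed to about 10-16% type I error for monthly decay of 0.54-0.9, about 9-10% under partial decay, and 6-11% for slope SDs of 0.05-0.15; it is correct under constant correlation. With categorical time the exposure lies mainly in the month-6 contrast (7-14%). All of this assumes complete data; missed visits were not simulated.

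PLF clustering is secondary: about 1-2 points of type I error at m = 5 and an assumed ICC of 0.05-0.10.

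**What to change.** In 5D.4:

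- State whether time is linear or categorical, and which interaction contrast is primary.
- Replace the subject random intercept with an unstructured 4x4 within-subject covariance, fitted by REML with Kenward-Roger degrees of freedom.
- Name in advance the fallback if that model does not converge, such as a random slope or a structure in which correlation decays with time.
- State as a limitation that group and clinician effects cannot be separated from PLF. Optionally, report a sensitivity interval over a range of ICCs and cluster sizes. Section 5C.6.2 already records which sessions each Veteran attends.

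The cost is a few sentences of analysis plan, somewhat wider intervals, and ten covariance parameters (four variances and six covariances) to estimate from 40 subjects, fewer with dropout. The last is the reason for the fallback.

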5C.6.3c. Exploratory Measure: **The Computer Adaptive Test version of the Community Reintegration of Injured Service Members measure (CRIS-CAT)**²⁶ consists of three scales measuring extent of, perceived limitations in, and satisfaction with community integration, has minimal patient burden and sound measurement properties including reliability, and predictive validity.

5D. Data Analytic Plan.

5D.1. Preliminary analyses. We will perform descriptive analyses to detect potential errors, check for missing data, identify outliers and ascertain whether there is sufficient dispersion for analyses, and that variable distributions accord with our statistical models. If the distribution of our

outcome measures does not accord with the assumptions of our statistical models, the appropriate power or logarithmic transformations will be used or we will create categorical variables as necessary. While patients were randomly assigned to our two study groups, we will also check for differences in demographics variables and baseline measures using chi-square tests, or t-tests, as appropriate.

5D.2. Missing Data. In handling missing data, all analyses will be intent to treat. For primary and secondary outcome measures, every effort will be made to assess all study participants at 1, 3 and 6-month time points. A direct likelihood approach in the analysis of mixed models²⁷ will be used. This method has the advantage of using all available data, and does not require any imputation.

5D.3. Analytic Strategy: Feasibility and Acceptability. Rates of recruitment, engagement, and attendance will be compared to published reports of similar type interventions. Acceptability will be analyzed with qualitative methods described in section 5C.6.2.

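### The exploratory ANCOVA leaves out baseline CRIS-CAT, which costs precision, and its rule for reading a significant interaction is false; the BSI visit and the word 'received' also need settling.

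*Combined protocol and SAP*

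**What the plan says.** Section 5D.4 gives the exploratory analysis in one paragraph: "For the Exploratory Aim, an Analysis of Covariance model with an interaction term will be used". On the outcome it says "In this model the outcome variable will be the CRIS-CAT score". On the predictors it says "the binary treatment variable will be whether the subject received PLF or TAU, the covariate will be the BSI". The remaining term is the product of treatment and BSI. No visit is named for either score, and no baseline CRIS-CAT term is listed.

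Two readings of the result are laid down in advance. Without an interaction, "the treatment effect will measure the distance between the parallel lines providing a measure of the improvement in community integration". With a significant interaction, "the improved community integration of one treatment group will be limited to a sub-range of the Beck scale".

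Elsewhere, Table 3 schedules both BSI and CRIS-CAT at baseline, month 1, month 3 and the follow-up three months later. Section 5C.6.3a makes BSI the primary outcome. Section 5C.6.3c says that CRIS-CAT "consists of three scales measuring extent of, perceived limitations in, and satisfaction with community integration". Section 5D.2 states "In handling missing data, all analyses will be intent to treat".

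**The concern.** Four features of the paragraph matter, and they do not carry equal weight.

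- **Baseline CRIS-CAT is left out.** The starting value of the outcome is usually the most useful covariate in an ANCOVA. It is collected here and not used, in a trial with 20 per arm.
- **The interaction rule is wrong.** A significant interaction shows that the slopes differ. It does not show where the lines meet, so it cannot by itself establish that benefit is confined to some BSI scores. An arm that does better at every observed score could be reported as better for only some Veterans.
- **The BSI visit is open.** BSI is also the primary outcome. If a value taken after randomisation were used, the treatment coefficient would hold fixed something that treatment is meant to change.
- **Treatment is worded as received.** This sits awkwardly beside the intent-to-treat statement.

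This paragraph is the only analysis given for the exploratory aim, and section 5D.5 says the pilot is meant to supply data for planning a larger study. An imprecise or misread result could carry over into that plan.

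**Working it through.** **1. The plan's own figure.** Section 5D.5 gives 80% power for an effect size of 0.91 with 20 per arm; 5D.4 sets a two-sided alpha of 0.05. For a two-sample t-test, df = 38 and the noncentrality is 0.91 × √(20/2) = 2.88. Power is 80.1%, and the effect detectable at 80% power is 0.909. The figure reproduces. It is not tied to the exploratory model, but it gives a yardstick for precision.

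**2. Leaving out baseline CRIS-CAT.** The documents give no CRIS-CAT standard deviation, correlation or expected effect, so the correlation r between baseline and outcome is an assumption, shown over a range. Adding the baseline multiplies residual variance by (1 − r²), and the detectable effect shrinks by roughly √(1 − r²). The last column is the exact noncentral t result with df = 37.

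| Assumed r | Fall in residual variance (r²) | 0.909 × √(1 − r²) | Detectable effect, exact |
|---|---|---|---|
| not used | – | – | 0.91 |
| 0.3 | 9% | 0.87 | 0.87 |
| 0.5 | 25% | 0.79 | 0.79 |
| 0.7 | 49% | 0.65 | 0.65 |

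These figures compare a model with no covariate to one with baseline CRIS-CAT. If baseline BSI is already in the model, r should be read as the correlation that remains after BSI is allowed for, so the gain may be smaller.

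**3. The interaction rule.** Write the arm difference at BSI score x as D(x) = b₁ + b₂x. The interaction test concerns b₂ only. The lines cross at x = −b₁/b₂, and nothing in the test places that point among the observed scores. For illustration take D(x) = 2 + 0.1x. The slopes differ, yet the lines cross at −2/0.1 = −20. Assuming that BSI scores are not negative (the documents do not give the scoring range), the difference is 2 at a score of 0 and 4 at a score of 20, and the same arm is better at every possible score. The rule therefore fails whichever BSI visit is used.

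**4. The BSI visit.** Suppose treatment lowers post-randomisation BSI by a, each unit of BSI lowers CRIS-CAT by b, and there is a direct effect d. The total effect is d + ab. Conditioning on post-randomisation BSI leaves d. All inputs are assumed: a = 0.5; b = 0.3, 0.5 or 0.7; d = 0 or 0.3. A simulation of 4,000 trials of 20 + 20 per scenario, with no interaction term, gave these mean estimates:

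| b | d | True total d + ab | Adjusted for baseline BSI | Adjusted for post-randomisation BSI |
|---|---|---|---|---|
| 0.3 | 0 | 0.15 | 0.149 | 0.000 |
| 0.5 | 0 | 0.25 | 0.252 | 0.002 |
| 0.7 | 0 | 0.35 | 0.346 | −0.004 |
| 0.3 | 0.3 | 0.45 | 0.445 | 0.294 |
| 0.5 | 0.3 | 0.55 | 0.551 | 0.302 |
| 0.7 | 0.3 | 0.65 | 0.650 | 0.299 |

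With an unmeasured common cause of BSI and CRIS-CAT added, the post-randomisation estimates fall further, to about −0.14 when d = 0 and 0.16 to 0.17 when d = 0.3. The estimates with baseline BSI stay within 0.01 of the truth in every scenario.

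The same simulation bears out step 2. Adjusting for baseline CRIS-CAT alone was also unbiased. In the first scenario its standard error was 0.209, against 0.261 unadjusted.

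**5. Treatment as received.** Section 5D.4 defines the treatment variable by what was received. Section 5D.2 applies intent to treat to all analyses, in a sentence that opens with missing data. No section sets an attendance threshold or a rule for moving Veterans between arms. The two texts are not aligned, but no as-treated procedure is described.

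**The case against.** A reader might go further and infer that the plan adjusts for post-randomisation BSI and so cannot estimate improvement at all. The documents do not support that. No visit is named, a baseline BSI is collected, and a baseline covariate is the ordinary use of ANCOVA. On that reading the arm contrast is unbiased, as step 4 shows. What stands is that the choice is left open and affects validity.

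A reader might also infer that any benefit on reintegration must come through reduced ideation, so that adjustment for later BSI would erase it. Table 1 points the other way: session 11 covers community reintegration directly, and sessions 5 and 6 cover friendship and interpersonal skills. A direct effect would survive the adjustment.

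Nor does leaving out baseline CRIS-CAT make the estimate invalid. The plan describes a contrast between arms, and randomisation keeps that contrast unbiased without the baseline value. This part is about precision only.

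Reading 'received' as an as-treated definition rests on one verb against a statement that all analyses are intent to treat. It is a wording conflict and no more.

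Finally, this is one exploratory measure in a 40-person pilot. That limits the importance of the point, but it does not rescue the interaction rule, which is wrong as written.

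**Conclusion.** Two points hold on any reading. The model leaves out a baseline measurement that is already scheduled, at a cost of about 9%, 25% or 49% of residual variance for assumed correlations of 0.3, 0.5 or 0.7. The sub-range rule does not follow from a significant interaction.

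A third point is conditional. If the BSI used is a post-randomisation value, the coefficient loses the part of the effect that passes through ideation. The sizes in step 4 rest wholly on assumed inputs; if the BSI used is the baseline value, there is no such bias. The conflict between 'received' and intent to treat needs reconciling but shows no error in the intended analysis.

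The primary and secondary analyses are untouched. The change is worth making because it is free and removes a conclusion that could be wrong.

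**What to change.** In the exploratory paragraph of section 5D.4:

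- Model post-baseline CRIS-CAT, at a named visit and on a named scale, on randomised arm, baseline CRIS-CAT and baseline BSI.
- If moderation is of interest, test arm by baseline BSI.
- Delete the sub-range rule. Report instead the estimated arm difference with its confidence interval across the observed range of baseline BSI.
- Write 'was randomised to' in place of 'received', so that the paragraph agrees with section 5D.2.

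The cost is a few sentences of analysis wording, best settled before outcome data are examined. Every variable is already collected, so there are no added visits, measures or participants.

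### Exploratory CRIS-CAT analysis (5D.4): a non-significant treatment-by-BSI interaction is in effect read as parallel lines and an effect over the whole BSI range, which 20 Veterans per arm cannot support (minor)

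*Combined protocol and SAP*

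**What the plan says.** Section 5D.4 sets out the exploratory model: "For the Exploratory Aim, an Analysis of Covariance model with an interaction term will be used". The outcome is the CRIS-CAT score, treatment is PLF or TAU, BSI is the covariate, and the interaction is treatment by BSI.

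Two branches follow. For the first: "If there is no interaction, then the focus will be on the treatment effect". The plan then says "In this situation the regression lines relating CRIS-CAT to BSI will be parallel" and describes the treatment effect as the gap separating them, "providing a measure of the improvement in community integration over the entire range of the BSI in subjects receiving PLF compared to patients receiving TAU". The second branch applies when the interaction is significant. The lines are then taken to intersect, and any advantage is confined to part of the BSI scale.

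The general testing rule in 5D.4 is: "All statistical tests will be two-tailed with an alpha =.05". Section 5C.5 gives the allocation: "A total of 20 Veterans are randomized to each group". The only power statement is in 5D.5: "With 20 subjects randomized to each of the two treatment groups, there will be 80% power to detect an effect size of 0.91". It concerns the comparison of two groups, not the interaction.

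The plan gives no interaction size that would matter, no confidence bound and no equivalence margin. It does not say which visit supplies the BSI covariate, although Table 3 schedules BSI at four visits.

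**The concern.** The data can show only that the interaction test is significant or that it is not. Because the second branch is defined by significance, the first branch can be entered only by a non-significant result. Failing to reject equal slopes is not evidence that the slopes are equal, least of all in a small trial. Yet the plan attaches a strong reading to that branch: parallel lines, and one treatment effect valid at every level of ideation.

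Suppose PLF improved reintegration mainly in Veterans with more severe ideation, or mainly in those with less. The trial could then describe one common effect over the whole scale when some Veterans gain nothing. Section 5D.5 says the pilot's data are meant to help plan a larger study, and a misleading statement about who benefits would be carried into that planning.

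**Working it through.** **Inputs from the documents.** 20 per arm (5C.5, 5D.5); two-sided alpha 0.05 (5D.4); 80% power at effect size 0.91 (5D.5).

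**Assumptions, not in the documents.** BSI is standardised, normal, equally spread in both arms and unaffected by treatment. CRIS-CAT residuals are normal with SD 1. Each Veteran contributes one CRIS-CAT score and none is missing. The slope difference g is in residual SDs of CRIS-CAT per SD of BSI.

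**Step 1: the plan's own figure.** Two-sample t-test, df = 2 × 20 − 2 = 38, noncentrality = 0.91 × √(20/2) = 2.88. Power is 80.1%, so the stated 80% reproduces. It says nothing about the interaction.

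**Step 2: precision of the slope difference.** The standard error is √(1/Sxx1 + 1/Sxx2), where Sxx1 and Sxx2 are the within-arm sums of squares of BSI. At their expected value of 19 it is √(2/19) = 0.324. Averaged over random BSI samples it is about 0.340. The test has 2 × 20 − 4 = 36 df, with critical t = 2.028. The 95% half-width is 2.028 × 0.340 = 0.69.

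So an estimated slope difference of exactly zero still leaves true differences up to about 0.69 in either direction compatible with the data. With a mean effect of 0.5 SD, a slope difference of 0.69 puts the PLF effect at 0.5 − 0.69 = −0.19 SD for Veterans 1 SD below mean BSI, and at 0.5 + 0.69 = 1.19 SD for those 1 SD above.

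**Step 3: how often the test misses a real interaction.** Power comes from the noncentral t with 36 df and noncentrality g / √(1/Sxx1 + 1/Sxx2), averaged over BSI samples.

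| True slope difference g | Non-significant, 20 per arm |
|---|---|
| 0.25 | about 89% |
| 0.5 | about 69% |
| 0.75 | about 42% |
| 1.0 | about 19% |

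Simulations agree to within about one percentage point. Power of 80% needs g of about 0.98.

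**Step 4: how often the misleading conclusion appears.** Take g = 0.5 with a mean effect of 0.5 SD. The PLF effect is then 0.5 − 0.5 = 0 at 1 SD below mean BSI and 0.5 + 0.5 = 1.0 SD at 1 SD above. In simulation, about 22% of all trials give both a non-significant interaction and a significant positive treatment effect.

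**Step 5: sensitivity to dropout.** The plan assumes none for this trial. Section 4.2 reports 59% completion in the team's DBT trial; 0.59 × 20 = 11.8, or about 12 per arm. At that size a slope difference of 0.5 is missed in about 81% of trials, and the joint event in step 4 occurs in about 17%.

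**The case against.** The wording is conditional: if there truly is no interaction, the lines are parallel by definition. The plan never writes that non-significance establishes this, and it calls the result a measure of improvement rather than a declared benefit. The aim is exploratory, the study is an admitted pilot, and 5D.5 is candid about its main effect size: "We recognize that this effect size is probably larger than the true effect size for these treatments".

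Most of this stands, and it limits the point. The plan does not claim proof of parallelism or commit to announcing a PLF benefit. The inference from non-significance is implied, by the contrast with a significant interaction and the lack of any other criterion. That is enough for a wording change, not for a charge against the trial's main results.

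Three stronger readings are tempting, and the documents do not support them:

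- **The test misses a material interaction two times in three.** That holds only for a slope difference near 0.5, a size found nowhere in the documents. Over 0.25 to 1.0 the miss rate runs from about 89% to 19%.
- **The plan will usually report a uniform benefit that is not there.** Even in the scenario of step 4, this happens in about 22% of trials.
- **The treatment effect would be read at BSI = 0**, because no step removes the interaction term or centres BSI. The same sentence of 5D.4 defines the effect as the separation of two parallel lines, which is the common-slope ANCOVA. At most, an explicit step to drop the term is missing.

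Nor do the documents say that this analysis will set enrolment criteria for the later study.

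**Conclusion.** The point holds as a minor one. In effect, 5D.4 moves from a non-significant interaction to equal slopes and an effect over the full BSI range, and 20 per arm cannot carry that step. The interval of about ±0.69 SD per SD shows this without deciding which interaction would matter; the miss rates depend on the slope difference assumed.

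The figures rest on roughly normal BSI with equal spread in both arms, full retention, and a covariate that treatment does not change. The last condition is reasonable for baseline BSI. It is doubtful for a later BSI score, because BSI is also the primary outcome, and the plan leaves the visit open. Only the interpretation of an exploratory aim is affected.

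**What to change.** In 5D.4, delete the statement that without a significant interaction the lines are parallel and the effect holds over the whole BSI range. Replace it with text to this effect:

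- Whatever the interaction p-value, the treatment effect is estimated from the ANCOVA without the interaction term, with baseline BSI as covariate, and is read as an average effect.
- A second model, with baseline BSI centred, gives the slope difference with its 95% confidence interval, together with PLF-TAU differences and 95% confidence intervals at low, median and high BSI.
- A non-significant interaction is not taken as evidence that the effect is the same at all BSI levels.

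The same passage should name the CRIS-CAT visit analysed, which is also left open.

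The cost is a few sentences and one table, with no new data or participants. The price is a less definite exploratory conclusion with wide intervals.
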